Visit 2- Screening visit Week 0 (+/- 14 days) This visit and all subsequent visits will only occur if participants have been found eligible to continue on the trial. It will include a 3 mm punch of skin; discussion about any medications they may be taking, a review of home blood glucose monitoring results, a review of adverse events and a review of insulin usage over 3 days prior to this visit. A urine sample will also be tested for pregnancy if the participant is female and of childbearing potential. The participants will be provided with a 3-month supply of the study drug/placebo. You will start TUDCA/placebo at a dose of 1750 mg orally daily.

Visit 3- Interim Visit (Month 1) (+/- 14 days) This in-person visit will include discussion about any medications the participant may be taking, review of home blood glucose monitoring results, a review of adverse events, and a review of insulin usage over 3 days prior to this visit. Blood tests will be done including liver function tests and a urine sample will also be tested for pregnancy if the participant is female and of childbearing potential. Participants will continue the study medication.

Visit 4- Interim Visit (Month 2) (+/- 14 days) This phone visit will include discussion about any medications participants may be taking, review of home blood glucose monitoring results, a review of adverse events, and a review of insulin usage over 3 days prior to this visit. Participants will continue the study medication.

Visit 5 - Interim Visit (Month 3) (+/- 14 days) This in-person visit will include a physical exam, a discussion about any medications the participant may be taking, review of home blood glucose monitoring results, a review of adverse events, and a review of insulin usage and blood glucose values over 3 days prior to this visit. The participant's blood will be drawn for liver function tests and HbA1c. A urine sample will also be tested for pregnancy if the participant is female and of childbearing potential. Participants will be provided with a 3-month supply of the study drug/placebo. Participants will continue the study medication.

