Visit 6- Interim Visit (Month 6) (+/- 14 days) This in-person visit will include a physical exam, a discussion about any medications the participant may be taking, review of home blood glucose monitoring results, a review of adverse events, and a review of insulin usage, and blood glucose values over 3 days prior to this visit. The participant will complete a 2 hr Mixed Meal Tolerance Test and have blood drawn for a HbA1c and liver function tests. A urine sample will also be tested for pregnancy if the participant is female and of childbearing potential. Participants will be provided with a 3-month supply of the study medication. Participants will continue the study medication.

Visit 7- Interim Visit (Month 9) (+/- 14 days) This in-person visit will include a discussion about any medications participants may be taking, review of home blood glucose monitoring results, a review of adverse events, and a review of insulin usage over 3 days prior to this visit. Participants will have blood drawn for a HbA1c and liver function tests. Participants will be provided with a 3-month supply of the study drug/ placebo. Participants will continue the study medication.

Visit 8- Interim Visit (Month 12) (+/- 14 days) This visit will include a physical exam, a discussion about any medications participants may be taking, review of home blood glucose monitoring results, a review of adverse events, and a review of insulin usage and blood glucose values over 3 days prior to this visit. Participants will complete a 2 hr Mixed Meal Tolerance Test and have blood drawn for a HbA1c and liver function tests. Medication will be stopped at the end of 12 months.

Visit 9- Interim Visit (Month 15) (+/- 1 month) This phone visit will include discussion about any medications participants may be taking, review of home blood glucose monitoring results, a review of adverse events, and a review of insulin usage over 3 days prior to this visit.

This in-person visit will include a physical exam, a discussion about any medications participants may be taking, review of home blood glucose monitoring results, a

review of adverse events, and a review of insulin usage and blood glucose values over 3 days prior to this visit. Participants will complete a 2 hr Mixed Meal Tolerance Test and have blood drawn for a HbA1c and liver function tests.

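### Month 9 is the only dispensing visit whose text lists no pregnancy test, and half of the dosing period follows the last listed test

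*Combined protocol and SAP*

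**What the plan says.** All references are to the combined protocol and SAP.

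Section 2 describes the study visit by visit. Three dispensing visits pair the supply with a urine pregnancy test:

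- Week 0 (Visit 2): "tested for pregnancy if the participant is female and of childbearing potential. The participants will be provided with a 3-month supply".
- Month 3 (Visit 5): "pregnancy if the participant is female and of childbearing potential. Participants will be provided with a 3-month supply of the study drug/placebo".
- Month 6 (Visit 6): "pregnancy if the participant is female and of childbearing potential. Participants will be provided with a 3-month supply of the study medication".

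Month 1 (Visit 3) has a test without a supply: "Blood tests will be done including liver function tests and a urine sample will also be tested for pregnancy". Screening also has a test, and a positive result there bars entry.

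Month 9 is attended in person: "Visit 7- Interim Visit (Month 9) (+/- 14 days) This in-person visit will include a discussion about any medications". Its laboratory and supply items read "Participants will have blood drawn for a HbA1c and liver function tests. Participants will be provided with a 3-month supply", with no pregnancy test. At Month 12 the text is "have blood drawn for a HbA1c and liver function tests. Medication will be stopped at the end of 12 months", again with no pregnancy test. Month 15 is by telephone: "Visit 9- Interim Visit (Month 15) (+/- 1 month) This phone visit will include discussion about any medications". The unheaded in-person visit described after it lists no pregnancy test either.

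Section 6.I, criterion 5, asks women with reproductive potential to be willing to avoid pregnancy and to have a negative test over the 12 treatment months and 3 months beyond. It sets no timepoints. Section 4.iii requires contraception throughout the study (abstinence, or two methods from a list that includes IUDs). Section 6 has subjects avoid estrogens and oral contraceptives.

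**The concern.** The plan treats pregnancy as incompatible with taking part, and it tests for it at every dispensing visit up to Month 6. Testing then stops halfway through dosing, and no reason is given. Month 9 has no practical obstacle to a test, because the participant attends and blood is drawn.

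What is at stake is fetal exposure to study drug. Following the visit text as written, a woman who became pregnant soon after the Month 6 test could be given three more months of drug at Month 9 with no listed test to reveal it. Because oral contraceptives are not allowed, contraception rests on abstinence, IUDs, and barrier or spermicide methods used in pairs. The same contraception rule was in force at the visits that do have a test, so the plan did not treat contraception alone as enough.

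This is a participant-safety point. It has no bearing on the C-peptide endpoint, the sample size or the analysis.

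**Working it through.** **1. Reproduce the plan's dosing length.** There are four supplies of 3 months (Week 0, Months 3, 6 and 9): 4 × 3 = 12 months. This equals the stated treatment duration, so the four dispensing visits account for all the drug.

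**2. Set tests against supplies (Section 2 visit text).**

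| Visit | Contact | Pregnancy test listed | 3-month supply |
|---|---|---|---|
| Screening | clinic | yes | no |
| Week 0 | clinic | yes | yes |
| Month 1 | clinic | yes | no |
| Month 2 | phone | no | no |
| Month 3 | clinic | yes | yes |
| Month 6 | clinic | yes | yes |
| Month 9 | clinic | **no** | **yes** |
| Month 12 | physical exam and blood draw | no | no (dosing ends) |
| Month 15 | phone | no | no |

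A same-visit test is listed at 3 of 4 dispensing visits. The exception is Month 9.

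**3. Age of the last listed test at each supply** (1 month = 30.44 days).

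- Week 0, Month 3, Month 6: 0 days.
- Month 9: 3 × 30.44 = 91 days. Visits 6 and 7 each have a ±14-day window, so the range is 91 − 28 = 63 to 91 + 28 = 119 days.

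**4. Stretches of dosing between listed tests.**

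- Week 0 to Month 1: 1 × 30.44 = 30 days.
- Month 1 to Month 3: 2 × 30.44 = 61 days.
- Month 3 to Month 6: 3 × 30.44 = 91 days.
- Month 6 to end of dosing: 6 × 30.44 = 183 days, which is 6/12 = 50% of treatment. With the Month 6 window alone the range is 183 ± 14 = 169 to 197 days. If the Month 12 visit also moves by 14 days, it is 183 ± 28 = 155 to 211 days.

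**5. Compare with criterion 5.** Its span is 12 + 3 = 15 months. The last listed test is at Month 6, so 15 − 6 = 9 of the 15 months have no listed test after it.

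**6. Effect of adding a Month 9 test.** Dispensing visits with a same-visit test rise from 3 of 4 to 4 of 4. The 183-day stretch splits into two of about 91 days, no longer than the nominal Month 3 to Month 6 gap. A Month 12 test falls at the end of dosing, so it can detect an exposed pregnancy but cannot shorten the exposure.

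**The case against.** The strongest reply is that this rests on silence in a schedule seen only in part. Section 2 points to a Trial Flow Diagram that is not in the available text and may list later tests. The visit narrative is itself untidy, with an in-person visit that has no heading after Month 15. Criterion 5 suggests that testing was not meant to end at Month 6, so the problem may be unaligned documentation and not a decision to stop testing. This stands as a limit on confidence. It does not remove the need for a correction: if the diagram does list the tests, site staff have two differing schedules and the visit text must be brought into line.

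Second, no passage makes supply depend on a negative test, and Month 1 shows that tests were not tied only to supply. That is correct, so this is a gap in the schedule and not a breach of a rule.

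Third, the harm is not quantified. The number of women who could become pregnant is not stated, about half of all subjects receive placebo under 1:1 allocation, contraception is required, and adverse events and medications are reviewed at Months 9, 12 and 15. The plan also already accepts about 91 days, and up to 119, between the Month 3 and Month 6 tests. All of this lowers the expected harm. None of it replaces a test, however, and Month 6 differs from Month 9 because a same-day test precedes the next supply.

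Finally, a test helps only if someone acts on it, and the documents state a consequence for a positive result only at screening. The point is fair but minor, and the revised text can settle it.

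**Conclusion.** The concern holds for the visit text as written. Month 9 is the only one of four dispensing visits without a listed same-visit pregnancy test. The last listed result is about 91 days old at that supply (63 to 119 days), and about 183 days of dosing, half of the treatment period, follow the Month 6 test.

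The gap should be closed, but it does not threaten the trial's conclusions. The number of women affected lies between 0 and 20, and the documents list no reproductive hazard for the drug. Confidence is medium, because the conclusion assumes that the Trial Flow Diagram does not already schedule later tests. The day counts assume a 30.44-day month and visits within the stated windows.

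**What to change.** 1. **Main change.** Add to Visit 7 (Month 9) the urine pregnancy-test sentence already used at Visits 2, 5 and 6. State that the test is done and read before the 3-month supply is given, and that a positive result means no further study drug.
2. **Second.** Add the same test to Visit 8 (Month 12), to detect a pregnancy already exposed to study drug.
3. **Criterion 5.** Either specify a home urine test reported at the Month 15 phone visit, or reword the criterion so that the 3 months after drug require only that pregnancy be avoided.
4. **Alignment.** Check the Trial Flow Diagram. If it already lists these tests, only the visit text needs correcting.

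Cost: one urine test per woman who could become pregnant, so at most 1 × 20 = 20 tests at Month 9, and at most 2 × 20 = 40 with Month 12. As an illustration, if 10 of the 20 subjects were such women (an assumption), the two visits would need 2 × 10 = 20 tests. The home-test option adds up to 20 more, and those results would be self-reported. No extra visit is needed, and the primary analysis does not change.

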Clinical Investigation of Efficacy of Tauroursodeoxycholic Acid (TUDCA) to Enhance Pancreatic Beta Cell Survival In Type 1 Diabetes by Reducing Endoplasmic Reticulum Stress

National Clinical Trial Identifier: NCT02218619

Document Date: March 9, 2021

1. Study Purpose and Rationale

Hypothesis: An agent (TUDCA) that reduces ER stress will protect against the deterioration of beta-cell function in new-onset T1D.

Rationale: Abnormalities of ER stress responses contribute to the beta cell failure in early-onset T1D. Treatment of pre-diabetic NOD mice with TUDCA preserves beta cell mass and insulin secretion (see Background). In mice, TUDCA treatment also decreases lymphocytic infiltration of the islets and improves survival and morphology of beta- cells. Patients with newly- diagnosed T1D have a residual beta cell mass of 30-50% (c-peptide often >0.2 pmol/mL); beta cell destruction continues for at least 12-24 months after diagnosis until C-peptide is generally low or undetectable.

In this pilot study in human subjects with T1D, we will enroll 20 new-onset (within 100 days of diagnosis) subjects with measurable stimulated C-peptide (>0.2 pmol/mL).

2. Study Design and Statistical Procedures Also see Trial Flow Diagram

Visit -1 -Screening visit (+/- 3 days) Each participant must sign a consent form prior to screening. The screening visit consists of a medical history, physical exam, assessment of other medications that they may be taking and a review of their insulin usage and blood glucose values over the previous three days, blood tests including liver function tests, a urine test and a combination 2 hour Mixed Meal Tolerance Test (MMTT).

For females only: A sample of their urine will be utilized for a urine pregnancy test during the screening. Only the participant will be told the results of this test. If the test is positive, then they will not be able to participate. Females who are lactating are also ineligible for this study.

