i. Endpoints: The primary endpoints will be the area under the stimulated C-peptide curve of a 2- hour mixed meal tolerance test (MMTT) conducted at screening, and during the 12 months of drug treatment at 6 and 12 months and at 6 months after drug or placebo is stopped.

The study will also examine as secondary endpoints the effect of the experimental treatment on diabetes-specific autoantibodies and metabolic parameters. Interim metabolic assessments will consist of periodic review of glucose records and reports of hypoglycemia, insulin dose and HbA1c.

- ii. Trial Design: This single-center double-masked, Phase II placebo-controlled study will examine the efficacy of TUDCA to arrest beta cell hypofunction/destruction in 20 subjects with new- onset T1D (ages 18-45 years), randomized within 100 days of diagnosis). All subjects will receive standard intensive diabetes treatment with insulin and dietary management, consistent with American Diabetes Association Standards of Care. Diabetes management will be done by the primary diabetes care team at the Berrie Center. Subjects will be randomly assigned 1:1 to receive either daily TUDCA 1750 mg/day or placebo for 12 months. All subjects will be followed for until study end and will be offered option for re-contact in the informed consent so that longer-term study follow-up is a possibility. Enrollment is expected to occur over 18 months. The mean c-peptide responses to MMTT in the TUDCA treatment group will be compared to the placebo-treated group at 0, 6, 12 and 18 months. The study will also examine the effects of TUDCA treatment on other T1D- related metabolic and immunologic outcome measures.
- iii. Exploratory outcome: If a significant change in c-peptide responses are detected in both groups, we will compare the *in vivo* responses to ER stress relief to in-vitro responses to ER stress relief. In these subjects, we will compare the clinical response to an agent that reduce ER stress to the response of the iPS-derived beta cells, derived from the same subject, when treated with the same experimental agent to reduce ER stress.

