- iv. Treatment and Dose: Subjects will be treated with either TUDCA at a dose of 1750 mg/day or placebo for 12 months with an additional 6 months of follow-up. 1750 mg is the most commonly used dose used to treat biliary disease and was used in a recent study of human obesity and insulin resistance (39). In this 4 week study, an effects on ER stress was not observed on adipose cells; however we plan a longer treatment time period and hypothesize that since TUDCA undergoes extensive

hepatic metabolism, the exposure of pancreatic beta cells to drug at this dose may be sufficient to cause an effect on ER stress. In addition, in vitro studies will enable us to manipulate exposure of beta cells to a range of TUDCA concentrations, thus revealing extent of individual differences in sensitivity to the agent.

v. Duration: All subjects will be followed for 1 year of treatment and at least 6 months of follow-up.

VI DSMB: The progress of the study will be monitored by the DSMB which will review safety data and make recommendations regarding continuation, termination, or modification of the study. Based on an 18 month enrollment period and an additional study period of at least 6 months, the DSMB will formally review the safety data, enrollment, and clinical outcome data at least twice yearly.

Vii The number of subjects who discontinue study treatment will also be included in the reports prepared for the DSMB.

Statistical analysis: These studies are pilots in which we anticipate substantial interindividual differences in responses to the proposed *in vivo* intervention (TUDCA). We will compare the clinical endpoints between treated and control subjects using repeated measures ANOVA, treating (if indicated) age, gender and BMI as covariates. The endpoints of the in vitro studies will be analyzed for differences between individuals regardless of the experimental group to which they have been randomized. These analyses will inform us of the range of autonomous beta cell differences in response to ER stress, and to the mitigation conveyed by TUDCA. These data will then be related to clinical endpoints, probing for the ability of the *in vitro* studies to predict (correlate with) clinical course and response to TUDCA. We are experienced in all of the relevant analytic techniques and have the software on hand. If necessary, we have access to expert statistical consultations through the Columbia NIH CTSA.

3. Study Procedures MMTT and skin biopsy

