- 4. Have any complicating medical issues or abnormal clinical laboratory results including abnormal liver function test (more than 1.5 x ULN) that interfere with study conduct or cause increased risk.
- 5. Have a history of malignancy.
- 6. Currently using non-insulin drugs that affect glucose control.
- 7. Currently using drugs that may interfere with TUDCA absorption or effect such as bile acid sequestering agents (cholestyramine and colestipol), aluminum based antacids, estrogens, oral contraceptives and clofibrate.
- 8. Currently participating in another T1D treatment trial or Sensitivity to TUDCA or other similar agent.
- iii.Subject withdrawal criteria: An intent—to-treat approach will be used. Subjects will not be replaced. All data acquired prior to termination for the reasons outlined below will be included in the primary analysis unless a participant withdraws consent. Every effort will be made to conduct a final study visit with the participant and participants will be followed clinically until, if applicable, all adverse events resolve. All subjects will be offered clinical follow-up at the Berrie Center for T1D.

Reasons for withdrawal and stopping rules: The drug will be stopped by the investigator because of serious and unexpected adverse events, safety laboratory parameters and/or vital signs. Subject may be withdrawn by the investigator; the subject my withdraw from the study; there may be an Intercurrent illness or event that precludes further to the study site or ability to evaluate disease.

Treatment of Subjects: Participants will be treated with either TUDCA at a dose of 1750 mg/day or placebo for 12 months, with study visits every 3 months during treatment, and undergo at least 6 months of follow-up, depending upon time of randomization. The study will be stopped based on occurrence of serious and unexpected adverse events, safety laboratory parameters and/or abnormal vital signs. Subjects will agree to avoid the following drugs during the study: non-insulin drugs that affect glucose control, bile acid sequestering agents (cholestyramine and colestipol), aluminum based antacids, estrogens, oral contraceptives and clofibrate. Subjects will be offered option of ongoing clinical care at Berrie Center for T1D as well as option for re-contact in informed consent, providing possibility for longer-term follow-up studies to be performed in the future on these subjects.

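### Section 6.iii does not separate stopping study drug from leaving the study, so early stoppers may have no later C-peptide tests and drop out of the intent-to-treat comparison

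*Combined protocol and SAP*

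**What the plan says.** All references are to the combined protocol and SAP.

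- **Section 2.i (Endpoints)** makes the MMTT C-peptide area the primary endpoint, measured at screening and then "at 6 and 12 months and at 6 months after drug or placebo is stopped".
- **Section 2.ii (Trial Design)** randomizes 20 subjects 1:1 and says that the mean responses "will be compared to the placebo-treated group at 0, 6, 12 and 18 months".
- **Section 2, Visit 8 (Month 12)** gives the planned end of treatment: "Medication will be stopped at the end of 12 months". Section 2.iv describes treatment "for 12 months with an additional 6 months of follow-up".
- **Section 2.v (Duration)**: "All subjects will be followed for 1 year of treatment and at least 6 months of follow-up".
- **Section 6.iii (Subject withdrawal criteria)** states an intent-to-treat approach without replacement. It continues: "All data acquired prior to termination for the reasons outlined below will be included in the primary analysis", unless consent is withdrawn. The reasons come in the next paragraph, which covers withdrawal and stopping rules together, and the first is that the investigator stops the drug. For these subjects the section provides an attempt at one last visit, with no timing or content, and clinical follow-up until any adverse events resolve.
- **Section 2 (Statistical analysis)** names repeated measures ANOVA and gives no rule for a subject with missing tests.

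**The concern.** Stopping the drug and leaving the study are different events. An intent-to-treat comparison needs outcome data after the first, and can lose them only through the second. Section 6.iii runs the two together: stopping the drug leads to termination, and nothing after termination is said to be measured or analysed. A site that follows this section could reasonably do no further MMTT once the drug has stopped.

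Two things are at stake. First, each later comparison could become one among subjects who tolerated and continued treatment, a group defined after randomization. If the reasons for stopping are related to the course of the disease or to the assigned treatment, the arms are no longer comparable. Second, each arm has only 10 subjects and none is replaced, so each lost subject is a tenth of an arm.

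**Working it through.** **1. The plan's own figure.** Planned stop at Month 12 (Visit 8) plus 6 months of follow-up (Section 2.iv): 12 + 6 = 18. This is the Month 18 of Section 2.ii. For everyone who completes treatment, Sections 2.i and 2.ii name the same visit.

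**2. The passages side by side for a subject whose drug is stopped early.**

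| Question | Section 6.iii | Elsewhere |
|---|---|---|
| Is the subject still in the study? | Stopping the drug is listed among the reasons for termination | Section 2.v: all subjects are followed through treatment and at least 6 months more |
| Are later MMTTs done? | One last visit, no time or MMTT stated | Section 2.ii compares arms at Months 6, 12 and 18 |
| Are later values analysed? | Only values from before termination are named | Section 6.iii itself states intent-to-treat |

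Early stopping is foreseen, since discontinuations are to be reported to the DSMB (Section 2, item vii). No section says what happens to these subjects' MMTTs.

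**3. Tests at risk.** Each arm has 20/2 = 10 subjects and three post-baseline MMTTs each, so 30 tests.

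- Stop before Month 6: up to 3 tests lost, 3/30 = 10% of the arm's post-baseline data.
- Stop between Months 6 and 12: up to 2 tests lost, 2/30 = 6.7%.
- Either way, Month 18 has 9 of 10 subjects.

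**4. Precision, as an illustration.** The documents give no alpha, power or standard deviation (SD). Assume a two-sided 5% test at one time point, a normal approximation, and the same number n observed in each arm. The difference detectable with 80% power, in SD units, is (1.960 + 0.842) × √(2/n). Power for a 1 SD difference is Φ(√(n/2) − 1.960).

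| n per arm | Detectable difference (SD) | Power for 1 SD |
|---|---|---|
| 10 | 1.25 | 61% |
| 9 | 1.32 | 56% |
| 8 | 1.40 | 52% |
| 7 | 1.50 | 46% |

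This shows lost precision only. The bias depends on who stops and why, which the documents do not let anyone compute.

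**5. A mistimed last test, only if the drug-stop clock is read literally.** For a stop at month s, six months later is month s + 6, which is g = 12 − s months before Month 18. With an assumed annual C-peptide loss d, that value reads high by (1 − d)^(−g/12) − 1. For s = 6, g = 6, and d = 20%, 35% or 50% gives 12%, 24% or 41%. One such subject in 10 would raise the arm mean by 1.2%, 2.4% or 4.1%. The loss rates and the stopping time are assumptions.

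**The case against.** **The timing sentences.** A reader might infer that Sections 2.i and 2.ii contradict each other, because one counts from drug stop and the other from randomization, and that early stoppers are therefore tested at the wrong point of a falling curve. The documents do not support this. Treatment has a planned stop at Month 12, and the natural reading of Section 2.i is that planned stop. The headed on-treatment and follow-up visits have fixed times. Nothing schedules an MMTT six months after an individual stop date, and nothing says that such a value would be entered as Month 18. Section 1 does say that "beta cell destruction continues for at least 12-24 months after diagnosis until C-peptide is generally low or undetectable", so an early test would tend to read high, but no such test is planned. This objection stands, and step 5 is illustrative only.

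**The data rule.** Section 6.iii says which data are included. It does not say that later data are excluded, and it sits beside an intent-to-treat statement. Section 2.v and the statement in Section 2.ii that subjects are followed to study end also point towards continued follow-up. This stands too: the sections are in tension and the plan is silent on tests after discontinuation, which is less than a contradiction. It does not settle the matter, because the section a site would consult when the drug is stopped offers only a last visit of unspecified content.

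**Differential stopping.** A reader might infer from the drug's gastrointestinal side effects that stopping will differ by arm. Section 4.i reports diarrhea, the commonest effect, in .01% of subjects, and no discontinuation rate is given. The documents give no basis for predicting an imbalance or its direction.

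**Conclusion.** The point holds as a gap in Section 6.iii. Because stopping drug is not separated from leaving the study, subjects who stop early may have no later MMTTs, and the Month 6, 12 and 18 comparisons could be limited to those who stayed on treatment. That is in tension with the intent-to-treat statement in the same section and with Section 2.v.

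From the documents alone, the size is at most 3 of 30 post-baseline tests in an arm for each early stopper. The precision figures rest on an assumed test and assumed losses. The bias has no computable size or direction without a discontinuation rate, a decline rate and an SD. The sponsor should close the gap because the remedy is cheap and each subject counts for a tenth of an arm. No existing result or timing rule has been shown to be wrong.

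**What to change.** In Section 6.iii, separate stopping study drug from withdrawing from the study, and state that:

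1. a subject who stops drug but has not withdrawn consent keeps the scheduled MMTTs at Months 6, 12 and 18, counted from randomization;
2. these values enter the intent-to-treat analysis in the arm assigned;
3. the date of last dose is recorded, so that time off drug can be described.

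For consistency, word the last MMTT in Section 2.i as Month 18. This is tidying, since it is already the same visit for everyone who completes 12 months of treatment.

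The cost is protocol wording. No test is added beyond those planned for every randomized subject, and the rules on when drug is stopped are untouched. The small downside is that a few subjects are asked to return for MMTTs after stopping drug.
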